8.3.3.3 EXPECTEDNESS

Site PI will be responsible for determining whether an adverse event (AE) is expected or unexpected. An AE will be considered unexpected if the nature, severity, or frequency of the event is not consistent with the risk information previously described for the study intervention.

8.3.4 TIME PERIOD AND FREQUENCY FOR EVENT ASSESSMENT AND FOLLOW-UP

The occurrence of an adverse event (AE) or serious adverse event (SAE) may come to the attention of study personnel during study visits and interviews of a study participant presenting for medical care, or upon review by a study monitor.

All AEs including local and systemic reactions not meeting the criteria for SAEs will be captured on the appropriate case report form (CRF). Information to be collected includes event description, time of onset, clinician's assessment of severity, relationship to study product (assessed only by those with the training and authority to make a diagnosis), and time of resolution/stabilization of the event. All AEs occurring while on study must be documented appropriately regardless of relationship. All AEs will be followed to adequate resolution.

Any medical condition that is present at the time that the participant is screened will be considered as baseline and not reported as an AE. However, if the study participant's condition deteriorates at any time during the study, it will be recorded as an AE.

Changes in the severity of an AE will be documented to allow an assessment of the duration of the event at each level of severity to be performed. AEs characterized as intermittent require documentation of onset and duration of each episode.

The site-PIs will record all reportable events with start dates occurring any time after informed consent is obtained until 7 (for non-serious AEs) or 30 days (for SAEs) after the last day of study participation. At each study visit, the investigator will inquire about the occurrence of AE/SAEs since the last visit. Events will be followed for outcome information until resolution or stabilization.

The main risks of bupropion include increased risk of seizure thus it should be used with caution in patient with an underlying seizure disorder, eating disorder, untreated alcohol use disorder, and/or concurrent use of a monoamine oxidase inhibitor (MAOI). Common side effects may include insomnia, dry mouth, and constipation. Uncommon side effects may include rash, itching or hives. The medicine may also cause dizziness thus individuals should avoid driving or using heavy machinery before they know how they might react. The medicine may also cause some patients to have abnormal behaviors or worsening mood or suicidal thoughts. Participants will be instructed to report any of these symptoms immediately to the research team.

8.3.6 SERIOUS ADVERSE EVENT REPORTING

Serious adverse events, whether related or unrelated, will be reported to the MPIs and the IRB as soon as study staff become aware of the event.

Reporting Events to Participants

Study participants will be notified individually of any new findings or adverse events which may affect their participation in the trial.

8.3.7 EVENTS OF SPECIAL INTEREST

N/A

8.3.8 REPORTING OF PREGNANCY

Prior to study participation, potential female participants are counseled to use birth control to prevent pregnancy during the trial. If a female participant becomes pregnant while on study, the PIs will determine if she should continue on study medication.

8.4 UNANTICIPATED PROBLEMS

8.4.1 DEFINITION OF UNANTICIPATED PROBLEMS (UP)

If any new risks to participants are identified, the following steps may be taken:

1. Modification of inclusion/exclusion criteria
2. Suspension of new enrollment or halting of study procedures for enrolled participants
3. Modification of informed consent document and/or protocol to include an explanation of the newly recognized risks.
4. Provision of additional information about newly recognized risks to enrolled participants.

Unanticipated problems may include any incident, experience, or outcome that meets the following criteria:

1. Unexpected in nature, severity, or frequency
2. Related or possibly related to study participation
3. Research participants or others are put at a greater risk of physical, psychological, economic, or social harm not previously known.

8.4.2 UNANTICIPATED PROBLEM REPORTING

The PI will report any unanticipated problem to the IRB and to the lead PI and include the following information:

1. Protocol number and title, name of PI
2. A detailed description of the event, incident, experience, or outcome.
3. A description of any necessary changes to the protocol or other corrective actions taken or proposed.

Unanticipated problems which are SAEs will be reported to the IRB and the lead PI with 48 hours of the PI becoming aware of the event. Unanticipated problems which are not serious will be reported within 7 days of the PI becoming aware of the event. In addition, the lead PI will report the unanticipated problem to the study sponsor as appropriate.

8.4.3 REPORTING UNANTICIPATED PROBLEMS TO PARTICIPANTS

Study participants will be individually notified of unanticipated problems if there are risks to their health or to their participation in the trial.

9 STATISTICAL CONSIDERATIONS

9.1 STATISTICAL HYPOTHESES

- Primary Efficacy Endpoint(s):

For our first primary hypothesis (Aim 1, Hypothesis 1), we will evaluate the impact of the initial treatment strategy (NRT vs NRT+CM) on daily cigarette consumption (self-reported mean cigarettes per day) at 12 weeks. We hypothesize that those receiving NRT+CM will have lower daily cigarettes consumed compared to those receiving only NRT.

In those not responding to the initial treatment, our second primary hypothesis is that switching to oral medication will lead to a greater reduction in average cigarettes per day at 24 weeks when compared to intensifying CM.

- Secondary Efficacy Endpoint(s):

We hypothesize that:

- 1) NRT+CM will be associated with higher rates of confirmed abstinence at 12 weeks compared to NRT only.
- 2) Among participants who do not respond to first stage treatment, switch to oral medication will be associated with higher rates of confirmed abstinence at 24 weeks compared to participants intensifying CM.

We do not have *a priori* hypotheses about HIV outcomes (i.e., CD4, HIV viral load, VACS Index) but will estimate the impact of the sequential treatment strategies on these outcomes.

Original Sample Size Calculation: The overall goal of this proposal is to identify the optimal dynamic treatment strategy for PWH who smoke cigarettes. The primary aims are to identify the most efficacious initial treatment (Aim 1, H1), verified with measurement of eCO or by next closest informant at 12 weeks, and the most efficacious treatment (switch vs intensify) for non-responders (i.e. participants who continue to smoke) to the initial randomization (Aim 2, H2), verified with measurement of eCO or by next closest informant at week 24. For the effect sizes of the treatments, VAR, combination NRT, and CM, we use effect sizes taken from a Cochrane meta-analysis of tobacco dependence treatment in PLWH, focusing on data pooled from 11 clinical trials involving a total of 1785 participants. In these studies, tobacco dependence treatment interventions (behavioral, pharmacologic, or both) had a Mantel-Haenszel risk of abstinence at up to 6 months, relative to controls, of 1.51 (95%CI 1.15, 2.00).¹ An additional Cochrane meta-analysis of incentive payments for smoking cessation in general populations of adult smokers, pooling data from 17 trials involving 7715 participants, found an odds ratio for abstinence at 6 months or more of 1.42 (95%CI 1.19, 1.69), relative to controls.² Using estimates from these studies, we assume a 12 week biochemically confirmed abstinence rate of 16% for the first-stage treatment of combination NRT+CM, and 7% for NRT alone. For the second stage, in which non-responders from both NRT and NRT+CM arms are randomized to 12 weeks of either switching medication or intensifying CM, we assume an end-of-treatment biochemically confirmed abstinence rate of 16% for switching, and 7% for intensifying. Given these parameters and a 2-sided type I error of 0.025 (corrected for 2 primary hypotheses) a total sample size of 538 participants will provide 85% power to detect superiority of NRT+CM over NRT alone for initial treatment. To account for a 15% loss to attrition, we will enroll a total of 632 participants. Given the expected proportions of non-response to initial treatment (i.e. 88.5% total; 84% and 93% in NRT+CM and NRT alone respectively), the sample size will provide 80% power to detect a difference of 9% (i.e. 16% in switch, 7% in intensify). The sample size calculation was performed with PASS v12 (Kaysville, UT). Analysis for Aim 1. Primary Study Endpoints and Analyses. The primary efficacy endpoint for this study will be biochemically verified 7-day cessation at 12 weeks (Hypothesis 1) and 24 weeks (Hypothesis 2).³ Tobacco use will be assessed by self-report and confirmatory biochemical testing with exhaled carbon monoxide.

9.3 POPULATIONS FOR ANALYSES

Intention to treat – all randomized participants will be included in the primary analysis of average cigarettes per day provided they have an assessment at either baseline and/or follow-up. In addition, all randomized participants will be included in the denominator for calculating abstinence rates with the exception of unavoidable loss to follow-up. This will include 1) participants who have died and 2) those documented to have moved to an untraceable address. We will report the number of participants in these categories who are excluded separately for each condition.⁴ Multiple imputation will be used to account for missing data in those who decline to be involved in subsequent data collection.

9.4 STATISTICAL ANALYSES

9.4.1 ANALYSIS OF THE PRIMARY EFFICACY ENDPOINT(S)

For our first primary hypothesis (Aim 1, Hypothesis 1), we will evaluate the impact of the initial treatment strategy (NRT vs NRT+CM) on daily cigarette consumption (self-reported average cigarettes per day) at 12 weeks. We hypothesize that those receiving NRT+CM will have lower daily cigarettes consumed compared to those receiving only NRT. A repeated measures mixed model will be used to compare the two treatment groups. The mixed model will jointly model baseline and 12-week daily cigarette consumption and will allow for the inclusion of all participants with at least one smoking assessment (Carpenter 2007). The model will include fixed effects for time and the interaction of treatment and time (i.e. no main effect of treatment) as well as age, gender and HSI. Random effects will be included for subject and site. Linear contrasts will be used to compare the difference between groups for week 12. This difference will be conditional on baseline consumption and is equivalent to an analysis adjusted for baseline (Carpenter 2007). The difference in 12 week cigarette consumption between treatment groups will be evaluated at the 0.025 significance level (i.e. Bonferroni corrected for the 2 primary hypotheses). 97.5% CIs will be estimated for treatment differences at week 12.

A similar repeated measures mixed model analysis will be used for our other primary hypothesis (Aim 1, Hypothesis 2), to evaluate the impact of the second randomization (i.e. switch vs intensify) in non-responders on average cigarettes per day. This analysis will only include participants who were non-responders to the initial treatment. For those non-responders initially randomized to NRT, switching refers to receiving VAR or bupropion in the second randomization while intensifying refers to receiving NRT+CM. For those non-responders initially randomized to NRT+CM, switching refers to receiving VAR or bupropion+CM in the second randomization while intensifying refers to receiving NRT+CM+. The repeated measures mixed model will include second stage treatment as well as covariates for site, age, gender, HSI, reason for 12-week non-response (i.e. non-abstainer vs. loss to follow-up) and initial treatment group. Differences in average cigarettes per day at 24 weeks and 97.5% confidence intervals will be estimated.

9.4.2 ANALYSIS OF THE SECONDARY ENDPOINT(S)

A logistic regression will be used including initial treatment (NRT vs NRT+CM) along with covariates for site, age, gender and HSI. Odds ratios, predicted probabilities of 12 week abstinence/reduction in smoking and 97.5% confidence intervals will be estimated. Multiple imputation by chained equations (MICE) will be used to impute missing abstinence outcomes. Baseline characteristics and abstinence outcomes assessed at other timepoints will be used in the missing data model. The difference between probabilities of 12 week abstinence/reduction between NRT and NRT+CM will be evaluated at the 0.025 two-sided significance level (i.e. Bonferroni corrected for the 2 primary hypotheses).

A similar analysis will be used for to evaluate the impact of the second randomization (i.e. switch vs intensify) in non-responders abstinence at 24 weeks. This analysis will only include participants who were non-responders to the initial treatment. For those non-responders initially randomized to NRT, switching refers to receiving VAR or bupropion in the second randomization while intensifying refers to receiving NRT+CM. For those non-responders initially randomized to NRT+CM, switching refers to receiving VAR or bupropion+CM in the second randomization while intensifying refers to receiving NRT+CM+. Logistic regression will include second stage treatment as well as covariates for site, age,

gender, HSI, reason for 12-week non-response (i.e. non-abstainer vs. loss to follow-up) and initial treatment group. Odds ratios, predicted probabilities of 24 week abstinence and 95% confidence intervals will be estimated. Multiple imputation by chained equations (MICE) will be used to impute missing abstinence outcomes. Baseline characteristics will be used in the missing data model. The difference between probabilities of 24 week abstinence between switching and intensifying will be evaluated at the 0.05 two-sided significance level.

For secondary outcomes of CD4 cell count, HIV viral load and VACS index weighted linear mixed models will be used to estimate mean outcomes at 12 and 24 weeks for each of the treatment strategies. A random effect will be included for repeated measures and the analysis will include indicators for first and second randomization, time, the interactions of first/second randomization indicators with time as well as covariates for baseline outcome, site, age and gender. Inverse probability weighting will be used to account for non-responders being re-randomized. Least squares means and 95% confidence intervals will be estimated. Evaluation of initial treatment strategies at 12 and 24 weeks will be performed using linear mixed models. These analyses will include fixed effects for initial treatment, time and their interaction as well as covariates for baseline outcome, site, age and gender and a random effect for subject to accommodate repeated measures. Similar linear mixed models of only non-responders will be used to evaluate second stage treatment.

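### Section 9.4.2 does not list randomized arm in either abstinence imputation model; followed as written, this dilutes the week-24 comparison of switching with intensifying

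*Combined protocol and SAP*

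**What the plan says.** The combined protocol and SAP handles missing abstinence data in Section 9.4.2: "Multiple imputation by chained equations (MICE) will be used to impute missing abstinence outcomes". It then gives a predictor list for each timepoint.

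- Week 12: "Baseline characteristics and abstinence outcomes assessed at other timepoints will be used in the missing data model".
- Week 24: "Baseline characteristics will be used in the missing data model".

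The analysis models are logistic regressions. The week-12 model has initial treatment, site, age, gender and HSI. The week-24 model has second-stage treatment, site and age, together with "gender, HSI, reason for 12-week non-response (i.e. non-abstainer vs. loss to follow-up) and initial treatment group". The week-24 set is restricted: "This analysis will only include participants who were non-responders to the initial treatment".

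Section 9.3 adds a general statement about imputation but no predictors: "Multiple imputation will be used to account for missing data in those who decline to be involved in subsequent data collection". No other section adds predictors.

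**The concern.** An imputation model should contain at least the variables in the analysis that uses its output, and above all the exposure being tested. If arm is absent, a missing outcome under switching and a missing outcome under intensifying are drawn from the same distribution, given the listed predictors. The imputed part of the data then carries no treatment effect, and the completed data show a smaller effect than the observed data do.

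At week 24 three terms of the analysis model are missing from the imputation list: second-stage arm, initial treatment group and reason for 12-week non-response. Both abstinence comparisons are stated hypotheses in Section 9.1 with significance levels in Section 9.4.2, so the bias would fall on tests that the trial intends to report.

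**Working it through.** **Inputs**

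- Stage 1 (Section 9.2): "abstinence rate of 16% for the first-stage treatment of combination NRT+CM, and 7% for NRT alone".
- Stage 2 (Section 9.2): "abstinence rate of 16% for switching, and 7% for intensifying".
- Loss to follow-up of 20% in the current design, and 250 projected non-responders from the table row with N = 282 (282 × 0.885 = 249.6) (Section 9.2).
- Two-sided 0.05 for week-24 abstinence (Section 9.4.2).
- Assumptions: second-stage allocation is 1:1 (the ratio is not stated), and the imputed share m is 10% to 30%.

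**Step 1: reproduce the plan's own abstinence figures.** For two proportions with pooled variance, two-sided alpha 0.025 and 85% power:

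n per arm = [2.241 × √(2 × 0.115 × 0.885) + 1.036 × √(0.16 × 0.84 + 0.07 × 0.93)]² / 0.09² ≈ 268.3, rounded up to 269.

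The total is 538, as stated, and 538 / 0.85 = 632.9 (632 stated). Non-responders are 538 × 0.885 = 476, which gives 80.1% power for the second stage (80% stated). The 16% and 7% are therefore the right inputs. The plan gives no figure for the imputation itself.

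**Step 2: expected difference at week 24 with arm omitted.** Randomization balances baseline characteristics, so imputing from them gives both arms the same average imputed rate p̄:

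D = (1 − m₁)(p₁ − p̄) + (1 − m₂)(p̄ − p₂)

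With equal missingness this is (1 − m)(p₁ − p₂), and p̄ = (16 + 7)/2 = 11.5%. At 20%:

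- switch: 0.8 × 16 + 0.2 × 11.5 = 15.1%
- intensify: 0.8 × 7 + 0.2 × 11.5 = 7.9%
- odds ratio: (0.151/0.849) / (0.079/0.921) = 2.07

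| Imputed share | Switch | Intensify | Difference (points) | Odds ratio |
|---|---|---|---|---|
| none | 16.0% | 7.0% | 9.0 | 2.53 |
| 10% | 15.55% | 7.45% | 8.1 | 2.29 |
| 20% | 15.1% | 7.9% | 7.2 | 2.07 |
| 30% | 14.65% | 8.35% | 6.3 | 1.88 |

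Unequal missingness does not remove the dilution. With 10% missing under switch and 30% under intensify, p̄ = (0.9 × 16 + 0.7 × 7)/1.6 = 12.06% and D = 0.9 × 3.94 + 0.7 × 5.06 = 7.1 points. The reverse pattern also gives 7.1. If p₁ = p₂, then p̄ equals both and D = 0, so the omission does not create an effect.

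**Step 3: power at week 24.** The simulation used 250 non-responders, 20% missing completely at random, 1,500 trials, 20 imputations, Rubin's rules and an unadjusted risk-difference test at 0.05. With arm omitted, the mean difference was 7.3 points and power 35%. With arm included, they were 9.1 points and 54%. A simpler simulation without covariates (4,000 trials, 10 imputations) gave 7.1 points and 34% against 8.9 points and 51%.

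**Step 4: which omission matters.** Dropout was then made to depend on week-12 smoking and on arm (250 non-responders, illustrative covariate strengths).

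| Imputation model | Mean difference (points) |
|---|---|
| neither arm nor week-12 smoking | 7.6 |
| week-12 smoking, no arm | 7.8 |
| arm, no week-12 smoking | 9.2 |
| both | 9.0 |

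Adding week-12 smoking data moves the estimate by about 0.2 points. Adding arm moves it by 1.2 to 1.6.

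**Step 5: week 12.** The upper limit at 20% missing is the full dilution, 9.0 − 7.2 = 1.8 points. The week-12 list includes abstinence at other timepoints. For participants seen at week 24, that outcome can carry back part of the initial-arm effect, so the attenuation lies between 0 and about 1.8 points. The power figures in Step 3 do not apply to week 12.

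**The case against.** The strongest reply is that the plan is silent on arm and does not exclude it. Neither predictor sentence says that the list is complete, and each follows a description of the analysis model, so it could be read as naming extra predictors. Initial arm might even count as a baseline characteristic. This stands in part: a careful programmer could add arm without contradicting the text, and a reader who infers a deliberate exclusion goes too far. But the two lists differ from each other, so they read as real content. Second-stage arm is assigned at week 12 and cannot be a baseline characteristic.

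Three other inferences are tempting, and the documents do not support them.

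- *The missing week-12 smoking data also cause the dilution.* Step 4 shows otherwise. Week-12 abstinence is nearly constant in this set anyway, because everyone in it is a non-responder.
- *Both hypotheses suffer the same dilution.* The full figure applies to week 24 only.
- *Sections 9.3 and 9.4.2 set conflicting rules.* Section 9.3 mentions imputation for people who decline further data collection, but it does not restrict imputation to them. It states no rule that counts unreachable participants as smokers. The wording is incomplete rather than contradictory.

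Two limits on size also stand. The 20% is total planned loss, and Section 9.3 removes deaths and untraceable moves from the abstinence denominator, so the imputed share may be lower. And power is modest even with arm included.

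**Conclusion.** The point holds as a gap in the specification. If the lists in Section 9.4.2 are followed as written, the week-24 abstinence difference shrinks by the imputed fraction, and on the plan's own rates roughly a third of the power is lost at 20% imputed (about 35% against just over 50%). At week 12 the effect is smaller and may be nil. The bias is toward no difference.

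The size rests on true rates of 16% and 7%, 1:1 second-stage allocation, and an imputed share of 10% to 30%, with 20% at the upper end of what the plan's loss assumption implies. The power figures come from an unadjusted test, not from the planned covariate-adjusted logistic model.

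Only the secondary abstinence analyses are affected. The primary mixed models for cigarettes per day in Section 9.4.1 do not use this imputation. The change is worth making because it removes an avoidable bias from two stated hypotheses.

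**What to change.** In Section 9.4.2, state that each imputation model includes every variable in its analysis model:

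- week 12: initial arm, site, age, gender and HSI, with abstinence at other timepoints kept as already planned;
- week 24: the same baseline terms and initial arm, plus second-stage arm and reason for 12-week non-response.

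Week-12 cigarettes per day may be added to the week-24 model as an auxiliary variable, itself imputed where missing, if the model is stable. Its purpose is precision and a more plausible missing-at-random assumption, not removal of the dilution. Stability needs checking. With 250 non-responders and 20% missing, about 200 outcomes are observed, with about 100 × 0.16 + 100 × 0.07 = 23 abstinent, and participants lost at week 12 will mostly lack week-12 values. Separate imputation by arm is not advised, since it would leave about 7 events in the lower arm.

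The cost is a sentence or two in the plan. Arm is known for everyone randomized, the other required variables are already in the analysis models, and no new data are needed.
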